2.1.4 Safety Endpoints

The safety endpoints are as follows:

- Incidence and severity of adverse events, with severity determined through use of the World Health Organization-Adverse Drug Reaction Terminology (WHO-ART)
- Change from baseline in vital signs, ECGs, and clinical laboratory results
- Incidence of anti-drug antibodies (ADAs)

2.1.5 Pharmacokinetic Endpoint

The PK endpoint is as follows:

- Serum concentration of MSTT1041A at specified timepoints

2.1.6 Exploratory Biomarker Endpoints

The key exploratory biomarker endpoints are as follows:

- Relative change in FeNO and blood eosinophils from baseline through Week 54
- Absolute levels of the soluble form of ST2-(sST2) in blood from baseline through Week 70

2.1.7 Exploratory Health Status Endpoints

The exploratory health status endpoint is as follows:

- Change in health status utility as assessed by the EuroQol 5-Dimension Questionnaire (EQ-5D-5L) from baseline to Week 54

2.2 DETERMINATION OF SAMPLE SIZE

A total of 502 patients were randomly allocated in a 1:1:1:1 ratio to receive one of three doses of MSTT1041A or placebo. This sample size provides approximately 80% power to detect a 40% reduction in the annualized asthma exacerbation rate (AER) between one MSTT1041A arm and the placebo arm, assuming 0.63 exacerbations per patient per year in the placebo arm, no Poisson over dispersion, a 15% dropout rate, and a two-sided significance level (α) of 0.05.

Enrollment caps are utilized to ensure adequate power for biomarker subgroup analysis based upon blood eosinophil status at visit 1. Approximately 30 eosinophil-high patients (≥ 300 cells/ μ L) per arm and approximately 95 eosinophil-low patients (< 300 cells/ μ L) per arm are randomly allocated. The sample size provides approximately 80% power to detect a 50% reduction in the annualized AER for the subgroup of eosinophil-high patients assuming 1.0 exacerbations per patient per year in the placebo arm, a 15% dropout rate, a two-sided significance level of 0.15, and 30 patients in each treatment arm having eosinophil-high status. The sample size also provides approximately 67% power to detect a 35% reduction in the annualized AER for the subgroup of eosinophil-low patients, assuming 0.5 exacerbations per patient per year in the placebo arm, no Poisson over dispersion, a 15% dropout rate, a two-sided significance level of 0.15, and 95 patients in each treatment arm having eosinophil-low status.

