6.1 DETERMINATION OF SAMPLE SIZE

A total of approximately 500 patients will be randomly allocated in a 1:1:1:1 ratio to receive one of three doses of MSTT1041A or placebo. This sample size provides approximately 80% power to detect a 40% reduction in annualized asthma exacerbation rate (AER) between one MSTT1041A arm and the placebo arm, assuming 0.63 exacerbations per patient per year in the placebo arm, a 15% dropout rate, and a two-sided significance level (α) of 0.05.

Enrollment caps will be utilized to ensure adequate power for biomarker subgroup analysis based upon blood eosinophil status at Visit 1. Approximately 30 eosinophil-high patients (≥ 300 cells/ μ L) per arm and approximately 95 eosinophil-low patients (< 300 cells/ μ L) per arm will be randomly allocated. The sample size provides approximately 80% power to detect a 50% reduction in annualized AER in the subgroup of eosinophil-high patients assuming 1.0 exacerbation per patient per year in the placebo arm, a 15% dropout rate, a two-sided significance level of 0.15, and 30 patients in each treatment arm having eosinophil-high status. The sample size also provides approximately 67% power to detect a 35% reduction in annualized AER in the subgroup of eosinophil-low patients, assuming 0.5 exacerbations per patient per year in the placebo arm, a 15% dropout rate, a two-sided significance level of 0.15, and 95 patients in each treatment arm having eosinophil-low status.

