The rate of asthma exacerbations will be compared between each active treatment arm and the placebo arm with the use of a Poisson regression model with over-dispersion. The primary analysis will be on the basis of observed exacerbations, with no imputation for premature study discontinuation. The Poisson regression model will include terms for treatment arm (three indicator variables, corresponding to the three treatment arms) and the baseline covariates described in Section 4.5. Patient time at risk will be used as an offset term in the model. The dispersion parameter will be estimated by Pearson's χ^2 statistic divided by its degrees of freedom.

Rates of asthma exacerbations adjusted for specified baseline covariates (see Section 4.5) will be estimated for each treatment arm with the use of the Poisson regression model. The ratio of exacerbation rates (for each MSTT1041A arm compared with the placebo arm) will be estimated from the Poisson regression model along with associated 95% CIs and p-values. The absolute difference in the exacerbation rates (for each MSTT1041A arm compared with the placebo arm, expressed as events per year) will also be provided, along with the associated 95% CIs.

See Sections 4.5.4, 4.5.5, and 4.5.6 for sensitivity, subgroup, and additional biomarker analyses that will be performed for the primary efficacy endpoint, respectively.

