early. An event count corresponding to each unobserved period will be imputed by first fitting a negative binomial generalized linear model to the observed data and sampling from the posterior distribution of the model parameter estimates. These sampled parameter estimates along with the patient-specific observed covariate values, observed exacerbation counts, and length of unobserved interval will be used in conjunction with a random number generator to impute an event count for the unobserved time period, which is added to the observed event count (Keene et al. 2014). These augmented datasets will be analyzed according to the model described in Section 4.5.1 and the results combined using Rubin's rules.

- In the tipping point sensitivity analysis, the underlying event rate used to impute unobserved event counts for a given arm will be adjusted via a multiplier delta; a separate delta will be applied to each arm. A range of delta values will be used to adjust the underlying event rate used for imputation in the MSTT1041A and placebo arms independently based on a grid of delta adjustments. The delta values will be chosen on the basis of the treatment effect (rate ratio) observed for a given MSTT1041A arm compared with placebo from the analyses described in Section 4.5.1. The range of delta values will include cases where dropouts from the MSTT1041A arm are assumed to have worse outcomes than dropouts from the placebo arm. For each endpoint, the resulting point estimates of treatment effect and corresponding p-values under each pair of deltas for each MSTT1041A and placebo comparison will be tabulated.

Also, for the secondary endpoint (absolute change from baseline in FEV₁), a cumulative responder plot which displays, by treatment arm, the proportion of patients who achieve each specified absolute change in pre-bronchodilator FEV₁ from baseline at Week 54 for a range of possible FEV₁ changes will be provided. For this plot, patients with missing Week 54 data will be assumed to be non-responders.

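### The stated 80% / 80% / 67% power holds only without over-dispersion, while the written test scales for it; the figures are best-case, and the condition is missing from most of the places that state them

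*SAP*

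**What the plan says.** SAP 2.2 puts the primary comparison at about 80% power for a 40% lower exacerbation rate on one active arm than on placebo, tested two-sided at 5%. Its inputs are given as "assuming 0.63 exacerbations per patient per year in the placebo arm, no Poisson over dispersion, a 15% dropout rate". The SAP repeats the no-over-dispersion condition for the eosinophil-low claim (67% power, 35% reduction, 95 per arm, significance level 0.15). The eosinophil-high claim (80% power, 50% reduction, 30 per arm) reads "assuming 1.0 exacerbations per patient per year in the placebo arm, a 15% dropout rate, a two-sided significance level of 0.15", with no mention of dispersion.

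Protocol 6.1 gives the same three powers. Its primary claim reads "assuming 0.63 exacerbations per patient per year in the placebo arm, a 15% dropout rate, and a two-sided significance level"; none of its three claims mentions dispersion. The protocol synopsis is worded in the same way.

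The analysis is a different matter. Protocol 6.4.1 and SAP 4.5.1 both specify Poisson regression with over-dispersion for the primary endpoint. SAP 4.5.1 also says how: "The dispersion parameter will be estimated by Pearson's", meaning the Pearson chi-square over its degrees of freedom. SAP 4.5.6 uses a similar model within the eosinophil subgroups. SAP 4.5.4 has a negative binomial re-analysis as a sensitivity check, and imputes unobserved counts after "fitting a negative binomial generalized linear model to the observed data". No section gives an expected dispersion, or power under one above 1.

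**The concern.** Estimating a dispersion φ and scaling by it multiplies every standard error by √φ. Power computed at φ = 1 therefore applies to the written test only if patients who share the same covariate values also share the same exacerbation rate. Any remaining between-patient variation pushes φ above 1 and lowers power. The covariates in SAP 4.5 are four coarse factors. Prior exacerbations, for example, enter as 1–2 versus 3 or more, although SAP 4.5.5 separates 1 from 2 for subgroup purposes.

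What is at stake is how a non-significant result is read. In SAP Table 1 the 490 mg comparison on the primary endpoint comes first, and each hypothesis is tested only if the one before it is significant, so a miss there ends formal testing. A reader who has only the protocol would weigh that miss against 80% power for a 40% reduction, with nothing on the page to say that 80% is the favourable end.

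**Working it through.** **Inputs** (SAP 2.2; 125 per arm from Protocol 4.1; one year of follow-up):

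| Claim | n per arm | Placebo rate/yr | Rate ratio | Two-sided α | Stated power |
|---|---|---|---|---|---|
| Primary | 125 | 0.63 | 0.60 | 0.05 | 80% |
| Eosinophil-high | 30 | 1.0 | 0.50 | 0.15 | 80% |
| Eosinophil-low | 95 | 0.5 | 0.65 | 0.15 | 67% |

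Dropout is 15% for all three. The dispersion φ is not given, so φ = 1.2, 1.5 and 2.0 are assumptions chosen to show a range.

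**Formula.** Expected events are m0 = n × 0.85 × rate in the placebo arm and m1 = m0 × RR in the active arm. SE0 = √(φ·2/m0), which takes the null variance at the placebo rate. SE1 = √(φ(1/m0 + 1/m1)). Power = Φ((|ln RR| − z·SE0)/SE1), with z = 1.960 at α = 0.05 and 1.440 at α = 0.15.

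**Step 1: reproduce the plan at φ = 1.**
- Primary: m0 = 125 × 0.85 × 0.63 = 66.94, m1 = 40.16, SE0 = 0.1729, SE1 = 0.1996. (0.5108 − 1.960 × 0.1729)/0.1996 = 0.862, so power is 80.6%. Using 125.5 per arm (502/4) gives 80.7%.
- Eosinophil-high: m0 = 25.5, m1 = 12.75, SE0 = 0.2801, SE1 = 0.3430. (0.6931 − 1.440 × 0.2801)/0.3430 = 0.845, so power is 80.1%.
- Eosinophil-low: m0 = 40.38, m1 = 26.24, SE0 = 0.2226, SE1 = 0.2507. (0.4308 − 1.440 × 0.2226)/0.2507 = 0.440, so power is 67.0%.

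All three printed figures come back. In this formula exposure and dispersion enter only as a ratio, so φ = 1/0.85 = 1.176 with full exposure would give the same values. Dispersion 1 follows because the plan states 15% dropout. This match is also what shows that the eosinophil-high figure carries the same unstated condition.

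**Step 2: let φ rise, all else fixed.** For the primary at φ = 1.2: SE0 = 0.1893, SE1 = 0.2186, (0.5108 − 1.960 × 0.1893)/0.2186 = 0.639, so power is 73.9%. At φ = 1.5: (0.5108 − 1.960 × 0.2117)/0.2445 = 0.392, so power is 65.3%.

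| φ | Primary | Eosinophil-high | Eosinophil-low |
|---|---|---|---|
| 1.0 | 80.6% | 80.1% | 67.0% |
| 1.2 | 73.9% | 74.8% | 61.4% |
| 1.5 | 65.3% | 68.2% | 55.0% |
| 2.0 | 54.5% | 60.0% | 47.5% |

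The primary loss from φ = 1.2 to 1.5 is 80.6 − 73.9 = 6.7 to 80.6 − 65.3 = 15.3 points.

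**Step 3: check against other forms of the test.** A Wald test replaces z·SE0 with z·SE1 and is lower throughout. At φ = 1 its primary power is 72.6% if dropouts contribute no exposure and 76.1% if they contribute half a year. With no exposure from dropouts it falls to 64.7% at φ = 1.2 and 55.2% at φ = 1.5, a loss of about 8 to 17 points. A four-arm simulation of the Pearson-scaled test (gamma-distributed patient rates, dropout spread uniformly over the year, no covariates, 4,000 runs) gave 77.2% at φ about 1.0, 70.0% at about 1.2, 65.4% at about 1.3 and 61.0% at about 1.4. The direction and approximate size of the loss do not depend on the formula.

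**The case against.** A reader might infer that the power figures are wrong, or that the sponsor hid the condition. Neither inference is supported. The figures reproduce exactly from stated inputs, and SAP 2.2 declares the condition in plain words for the primary claim and for eosinophil-low. The SAP also says that it supersedes the protocol's high-level analysis plan, so the document that discloses is the governing one. The single SAP omission is on an exploratory subgroup with no type I error control.

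A reader might also infer that the plan expects material over-dispersion because it uses negative binomial models. That goes too far. One of them is offered as a robustness check and the other is an imputation device, and neither comes with an expected value. The range 1.2 to 1.5 is this review's assumption. The simulation above has no covariates, whereas the planned model adjusts for eosinophils, prior exacerbations, inhaled corticosteroid dose and region, which may bring residual dispersion closer to 1.

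Finally, all 502 patients are already randomized. The estimate, the test and the type I error are unaffected, and the 95% confidence intervals for the rate ratios will show which effects a non-significant result leaves open.

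All of this stands, and it limits the point to one of statement. It does not remove the gap: no figure in either document is the power of the test that decides success, unless the dispersion is exactly 1.

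**Conclusion.** The point holds as a mismatch between the stated power and the written test. The 80% / 80% / 67% figures are best-case values. The condition behind them is named for two of the three SAP claims and for none of the protocol's. If residual dispersion lies between 1.2 and 1.5, primary power is about 74% to 65% by the formula that reproduces the plan. The subgroup powers fall by about 5 to 12 points over the same range (eosinophil-high 80.1% to 74.8–68.2%, eosinophil-low 67.0% to 61.4–55.0%). If the covariates absorb most of the between-patient variation, the loss is smaller, and at dispersion 1 it is nil.

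A separate caution is that the reproducing formula sets its null variance at the placebo rate. A Wald test with the same inputs has 73% to 76% primary power even at dispersion 1, so the shortfall from 80% could exceed the over-dispersion loss alone.

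**What to change.** In SAP 2.2, before the 54-week analysis closes the SAP to changes, state the no-over-dispersion condition on all three claims and add power by dispersion with the 15% dropout included. At dispersion 1.0 / 1.2 / 1.5 / 2.0 the rows would be:
- primary: about 81 / 74 / 65 / 54%
- eosinophil-high: about 80 / 75 / 68 / 60%
- eosinophil-low: about 67 / 61 / 55 / 47%

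Add one sentence saying that the formula takes its null variance at the placebo rate and that a Wald test gives lower power. Make the same change to Protocol 6.1 and the synopsis if the protocol is amended for another reason.

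No change to enrolment or to the analysis model is needed. A dispersion estimate from pooled blinded counts would show which row applies, but it is optional because it changes no decision, and pooling slightly overstates within-arm dispersion if the drug works. The cost is a few lines of text and a stated power that looks less favourable.

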2.3 ANALYSIS TIMING AND UNBLINDING

Analysis of data from the 52-week double-blind treatment period of the study, defined as the time of randomization (Week 2) through the Week 54 visit, will be performed when all patients either (i) have completed the Week 54 visit, (ii) have discontinued treatment early from the 52-week double-blind treatment period of the study but completed follow-up visits up to 52-weeks post-randomization, or (iii) have withdrawn from the

study prior to Week 54, and all data from the first 54 weeks of the study are in the database and have been reviewed.

At the time of the primary analysis, the Sponsor personnel who are analyzing data from the first 54 weeks of the study will be unblinded to treatment assignment. This includes personnel directly involved in the statistical analyses and programming activities as well as Sponsor personnel from other functions (e.g., Clinical Science, Safety Science, Clinical Pharmacology, and Regulatory Affairs) who will be involved in assessing, summarizing, and interpreting the data.

The analysis of complete data for the study, including data from the safety follow-up period, will be performed when all patients have either completed the safety follow-up period or have discontinued early from the study, all data from the study are in the database, and the database is locked.

Aggregate results of the primary analysis, summarized by treatment arm and potentially biomarker group, may be reported to the public before completion of the study. However, patients and study site personnel will remain blinded to individual treatment assignment until after the study is completed (after all patients have either completed the safety follow-up period or discontinued early from the study), the database is locked, and the study analyses are final.

2.4 DATA INCLUDED IN WEEK 54 DATA CUT

The following data will be included in the Week 54 data cut:

- **For patients randomized to the 52-week double-blind treatment period:** All screening, run-in and post-baseline data with a clinical date (i.e., administration/assessment/onset/start date) on or before the date of randomization to Week 54 will be included.
- **For patients not randomized to the 52-week double-blind treatment period:** All screening and run-in data with a clinical date (i.e., administration/assessment/onset/start date).

The Week 54 data cut will include all data regardless of the type of study visit at which it was collected. This may include data collected at unscheduled visits, dosing termination visits, early termination visits, or safety follow-up visits, if the visit date was on or before the Week 54 data cutoff date.

3. STUDY CONDUCT

3.1 RANDOMIZATION ISSUES

Following successful completion of the run-in period, at the Week 2 visit, patients were randomly allocated to one of four treatment arms (MSTT1041A 70 mg, MSTT1041A 210 mg, MSTT1041A 490 mg, or placebo) in a 1:1:1:1 ratio through an interactive voice or web-based response system (IxRS). Randomization was stratified by blood

eosinophil status at visit 1 (< 150, ≥150 to <300, ≥300 cells/μL), number of documented asthma exacerbations (as defined in [Appendix 5](#)) in the previous 12 months (1-2, ≥3), total daily ICS dose at visit 1 (< 1000 μg, ≥ 1000 μg of fluticasone proportionate or equivalent), and country. A dynamic randomization method is used to obtain an approximately 1:1:1:1 ratio between the four treatment arms and within each stratum.

During both the run-in and the 52-week double-blind treatment periods, the IxRS will make study-drug kit assignments. Patient randomization and the study-drug kit assignments will be verified on an ongoing basis by an external and independent data coordinating center (iDCC). The iDCC independently reviews the logs to ensure that randomization and kit assignments are conducted correctly by the IxRS.

3.2 DATA MONITORING

An independent Data Monitoring Committee (iDMC) will monitor safety and study conduct on an ongoing basis. Members of the iDMC are external to the Sponsor and follow procedures that are detailed in a Charter that outlines the iDMC roles and responsibilities. The iDMC will meet approximately every 3 months to review unblinded safety and study conduct data prepared by the iDCC. In addition, the iDMC or the Sponsor may request ad hoc reviews at any time to address potential safety concerns.

Safety monitoring reviews include unblinded evaluation of all adverse events, serious adverse events, adverse events of special interest, major protocol deviations, ECG, and laboratory data. If the iDMC deems a benefit-risk assessment necessary, the iDMC may also review unblinded efficacy data. The iDMC may recommend stopping the study early for safety reasons. However, the iDMC may not recommend stopping the study early for positive efficacy or solely for futility. Formal stopping guidelines for assessing safety or the balance between the risks and benefits related to continuing the study will not be provided by the Sponsor. The iDMC will use its collective judgement to recommend early termination of the study if the data indicate an unacceptable safety profile. Details will be provided in the iDMC Charter.

4. STATISTICAL METHODS

4.1 ANALYSIS POPULATIONS

Three analysis populations are defined for this study: the modified intend-to-treat (mITT) population, the safety-evaluable population, and the run-in safety-evaluable population.

4.1.1 Modified Intend-to-Treat Population

The mITT population will include all patients who were randomly allocated and received at least one dose of study drug (MSTT1041A or placebo) during the 52-week double-blind treatment period (Week 2 through Week 54). For analyses based on this population, patient treatment groups will be defined according to the treatment that was assigned at randomization (placebo, MSTT1041A 70 mg, MSTT1041A 210 mg, or MSTT1041A 490 mg).

4.1.2 Safety-Evaluable Population

The safety-evaluable population will include all patients who were randomly allocated and received at least one dose of study drug (MSTT1041A or placebo) during the 52-week double-blind treatment period (Week 2 through Week 54) with treatment groups defined according to the actual treatment received.

Because each patient can receive up to 13 doses of study drug during the 52-week double-blind treatment period, the treatment received will be defined as the study treatment (placebo, MSTT1041A 70 mg, MSTT1041A 210 mg, or MSTT1041A 490 mg) most frequently given to the patient during the double-blind treatment period. In the event that this is not unique, treatment received will be defined as the highest of the most frequently given dose levels (e.g., a patient who receives 1 dose of placebo and 1 dose of MSTT1041A 70 mg would be assigned to the MSTT1041A 70 mg treatment group for analyses based on the safety-evaluable population).

It is expected that most patients will receive their assigned treatment at all dosing timepoints and that only a small number of dosing errors, if any, will occur. Nonetheless, each dosing error will be reported as a major protocol deviation and reviewed in conjunction with the corresponding patient's safety data to assess for any impact on the overall safety conclusions.

4.1.3 Run-In Safety-Evaluable Population

The run-in safety-evaluable population will include all patients who received the single-blind placebo dose during the run-in period (Week 0 treatment), regardless of whether or not the patient is randomly allocated into the double-blind treatment period. For safety analyses based on this population, only events that occur during the 2-week run-in period will be included. As placebo should be the only study drug administered during the run-in period, all patients will be grouped together for analyses based on this population.

In the rare event that a patient mistakenly receives MSTT1041A rather than placebo during the run-in visit, each dosing error will be reported as a major protocol deviation and reviewed in conjunction with the corresponding patient's safety data to assess for any impact on the overall safety conclusions.

